5 IDENTIFICATION AND DESCRIPTION OF THE DEVICE

5.1 Device description

The Ponto Softband device is part of a skin-drive bone conduction, wherein a Ponto sound processor is attached to the band which allows for circumlocution of the function of the outer and middle ear. Acoustic sound pressure waves are picked up by the microphones in the externally mounted sound processor and this signal is converted to mechanical energy (vibrations) by the transducer in the sound processor. This signal is then transmitted through the skin to the temporal bone of the skull. The mechanical energy vibrates the temporal bones of the skull which are picked up by the hair cells within the cochlea in the inner ear where the mechanical energy is converted to electrical neural impulses and transmitted to the primary auditory cortex in brain via the auditory nerve.

The survey will focus on Softband 5 but will also allow for feedback from parents whose children previously or currently use any of the Softband generation models:

- Softband/Softband bilateral (initial CE 2010)

- Ponto Softband (initial CE 2016)
- Ponto Softband bilateral (initial CE 2017)
- Softband 5 (initial CE 2022)

Parents whose children have been fitted with a Ponto sound processor on a Ponto Softband will be surveyed.

The study will focus on devices from the following Ponto families:

- Ponto 3, Ponto 3 Power, Ponto 3 SuperPower
- Ponto 4
- Ponto 5 Mini, Ponto 5 SuperPower

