a) much better b) a little better c) no change d) a little worse e) much worse

19. Has your child's Ponto sound processor on softband affected his/her confidence?

a) much better b) a little better c) no change d) a little worse e) much worse

20. Has your child's Ponto sound processor on softband affected his/her ability to care for him/herself as well as you think he/she should, such as washing, dressing, and using the toilet?

a) much better b) a little better c) no change d) a little worse e) much worse

21. Has your child's Ponto sound processor on softband affected his/her ability to enjoy leisure activities such as swimming and sports and general play?

a) much better b) a little better c) no change d) a little worse e) much worse

22. Has your child's Ponto sound processor on softband affected how often he/she needs to visit a doctor?

a) much better b) a little better c) no change d) a little worse e) much worse

23. Has your child's Ponto sound processor on softband affected how prone he/she is to catch colds or infections?

a) much better b) a little better c) no change d) a little worse e) much worse

24. Has your child's Ponto sound processor on softband affected how much medication he/she has needed to take?

a) much better b) a little better c) no change d) a little worse e) much worse

C. Softband specific questionnaire**1. Is your child currently using a Ponto sound processor on a softband?**

Yes

No

2. What is your child's date of birth? (Please use MM/DD/YYYY format)

 /

 /

3. What is your child's gender?

Male

Female

Other

Do not wish to disclose

4. Approximately how long has your child experienced hearing problems?

Less than a year

1 to 3 years

3 to 6 years

6 to 9 years

more than 9 years

I'm not certain

Since birth

5. How long has your child been using a Ponto sound processor on softband?

Less than a year

1 to 3 years

3 to 6 years

6 to 9 years

more than 9 years

I'm not certain

Since birth

6. Is your child using one or two Ponto sound processor(s)?

1 – One sound processor

2 - Two sound processors (one on the left, one on the right)

7. Is your child currently using a Softband 5 or other softband?

Softband 5

Other softband

I'm not sure

8. Is this your child's first softband?

Yes, this is the first

No, they used a different generation softband in the past

I'm not sure

9. Which Ponto sound processor does your child currently use?

Ponto 3

Ponto 3 Power

Ponto 3 SuperPower

Ponto 4

Ponto 5 Mini

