Ponto 5 SuperPower

I don't know / other model

10. Think about how much your child used their sound processor(s) over the past two weeks. On an average day, how many hours did they use the sound processor(s)?

none
less than 1 hour a day
1 to 4 hours a day
4 to 8 hours a day
more than 8 hours a day

**11. Think about a situation where your child wanted to hear better, before receiving their sound processor.
Over the past two weeks, how much has the sound processor(s) helped in that situation?**

helped not at all
helped slightly
helped moderately
helped quite a lot
helped very much

12. How satisfied overall are you with your child's Ponto experience?

very much
quite a lot
moderately
slightly
not at all

13. How satisfied overall are you with your child's softband?

very much
quite a lot
moderately
slightly
not at all

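### Q8 of the softband questionnaire has no true answer for a child whose earlier softbands were all of the same generation as the current one, so any such family is misfiled

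*Combined protocol and SAP*

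**What the plan says.** Appendix C, the sponsor's own softband questionnaire, asks "8. Is this your child's first softband" and offers three answers: "Yes, this is the first", "No, they used a different generation softband in the past", and an option for parents who are not sure. The appendix shows no free-text field, skip rule or completion note for this item.

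The two nearest items are Q7, "7. Is your child currently using a Softband 5 or other softband", and Q5, "5. How long has your child been using a Ponto sound processor on softband". Q7 concerns the present band only. Q5 gives total time on a softband, without the number of bands or their generations.

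Section 5.1 focuses the survey on Softband 5 and also accepts feedback from "parents whose children previously or currently use any of the Softband generation models". Section 11 plans descriptive statistics for the questionnaires, names no subgroup or split, and rules out imputation. Section 9.1.3 sets the target at 40 participants.

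**The concern.** The stem and the answers ask different things. The stem asks about any earlier softband. The single negative answer adds a second condition, that the earlier band was of another generation. A family that simply replaced a band with another of the same generation meets the stem's 'no' but not the added condition.

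Such a parent must give an untrue answer or skip the item. A 'yes' inflates the first-band count, a 'no' inflates the changed-generation count, and a not-sure answer or a skip removes the family from both. The direction cannot be known from the data. At stake is the accuracy of one descriptive count in the sponsor's questionnaire, and of any grouping by softband history that someone might later build on it.

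**Working it through.** The plan has no figure that depends on Q8, so there is none to reproduce. The check has a logical part and a count illustration.

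**Step 1: match histories to answers** (Appendix C, Q8).

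| True history | True Q8 answer available? |
|---|---|
| No earlier softband | Yes: the first option |
| At least one earlier band of a different generation | Yes: the second option |
| Earlier band(s), all of the same generation as now | None |
| Parent does not know | Yes: the not-sure option |

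Three of the four histories have a true answer.

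**Step 2: can other items repair it?** Section 5.1 dates the initial CE mark of Softband 5 to 2022. A child now on Softband 5 (Q7) whose softband use began before then (Q5) must have worn an earlier generation. That identifies some changed-generation families. It cannot tell a first band from a same-generation replacement, because Q5 and Q7 can read identically for both.

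**Step 3: size.** Inputs: N = 40 (Section 9.1.3). The share s of same-generation-only families is not in the documents, so it is assumed from 0% to 30%. The remaining families are assumed to split 60:40 between first-band and changed-generation, with none unsure.

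- Weight of one family: 1/40 = 2.5 percentage points.
- Families with no true answer: m = 40 × s.
- First-band share if all m answer 'yes': (true first + m)/40.
- Changed-generation share if all m answer 'no': (true changed + m)/40.

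| s | m | True first / changed | First-band if all answer 'yes' (true) | Changed if all answer 'no' (true) |
|---|---|---|---|---|
| 0% | 0 | 24 / 16 | 24 = 60% (60%) | 16 = 40% (40%) |
| 5% | 2 | 23 / 15 | 25 = 62.5% (57.5%) | 17 = 42.5% (37.5%) |
| 10% | 4 | 22 / 14 | 26 = 65% (55%) | 18 = 45% (35%) |
| 20% | 8 | 19 / 13 | 27 = 67.5% (47.5%) | 21 = 52.5% (32.5%) |
| 30% | 12 | 17 / 11 | 29 = 72.5% (42.5%) | 23 = 57.5% (27.5%) |

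These are the extremes. A mixture of answers gives smaller shifts in each category, and not-sure answers inflate neither group.

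The chance that at least one such family enrols is 1 − (1 − s)^40. At s = 5% this is 1 − 0.95^40 = 87%, and at s = 10% it is 1 − 0.90^40 = 98.5%.

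**The case against.** The strongest reply is that no miscount is shown. The documents give no replacement rate, and Section 4.1 describes the band as adjustable, which weakens the idea that children outgrow it. The longest category in Q5 is no evidence of replacement, because Q4 uses the same list of durations. Long use could equally mean a change of generation, which Q8 does capture. Coming straight after Q7, Q8 might also be read as asking about the first generation used. Parents of same-generation users would then answer 'yes' and the changed-generation count would be right. All of this stands as a limit on size. It does not supply the missing answer, and under that last reading the first-band count is still not a count of first bands.

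Three stronger readings are tempting, and the documents do not support them.

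- A reader might infer that the benefit or satisfaction results rest on mislabelled groups. Section 11 plans no analysis by Q8, and the Softband 5 focus is served by Q7.
- A reader might infer that a primary endpoint is damaged, since the synopsis lists the outcomes of the satisfaction questionnaire. The help and satisfaction ratings are Q11 to Q13, and Q8 does not enter them.
- A reader might take Section 5.1 as promising a comparison of old and new bands, which "How satisfied overall are you with your child's softband" (Q13) cannot give. Section 5.1 states whose feedback is accepted. It promises no band-to-band comparison, so the lack of one is not a failure against the plan.

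**Conclusion.** The response gap is real and visible on the face of the item, and no other item closes it. The conclusion that some families have no true answer needs no assumption beyond a parent who knows the history.

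The size is unknown and may be zero. Each such family shifts a category by 2.5 percentage points at N = 40, and the tabulated shifts rest entirely on the assumed shares and the assumed 60:40 split. I take the descriptive presentation in Section 11 to include the Q8 distribution. The harm stops there and at any later, unplanned split by softband history. This is a minor point, worth making because the correction is nearly free.

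**What to change.** Before launch, add one option to Q8 and leave the other three as they are: *No, they used an earlier softband of the same generation*. A child with both kinds of earlier band could truthfully choose either 'no', so adding *only* to the new option would keep the two apart. With that, each history in Step 1 has exactly one true answer, and misfiling from this cause falls to zero at any assumed share. In the 10% illustration the item would return 22 first-band, 14 changed-generation and 4 same-generation families.

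Keep the word 'generation'. Changing it to 'model' would alter what Q8 measures, because Section 5.1 lists the Ponto Softband and its bilateral version separately. No new comparison item is needed.

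The cost is one more answer option for parents to read. The questionnaire is the sponsor's own, so neither PEACH nor GCBI is touched.

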6 JUSTIFICATION FOR THE INVESTIGATION

The study is a non-interventional, observational, study on users of Ponto sound processors who use their sound processors on a softband solution. The purpose of this study is to assess subjective benefit by evaluating performance and overall satisfaction of the Ponto on a Ponto Softband in pediatric users.

This study will utilize responses from survey questions of parents or primary caregivers of children fitted with a softband solution. The survey will collect responses relating to reported hearing improvements and quality of life.

The study will use the PEACH questionnaire¹ to evaluate performance. The PEACH is a measure used by hearing health professionals to evaluate the effectiveness of a child's use of hearing in real-world environments. PEACH is validated with norms scale (English). This study will also use the GCBI questionnaire², modified to specifically query a child's quality of life after receiving their Ponto sound processor on softband. Additionally, a specialized questionnaire is constructed to gather feedback on wear and general comfort of Oticon Medical Softband.

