9.1.1 Inclusion criteria

The following participants will be included in the study:

	Title BC117 - Pediatric Performance and Satisfaction of Oticon Medical Ponto on Softband	Document no Doc-00121767	Revision 0	Page 8(17)
---	--	------------------------------------	----------------------	----------------------

- Individuals who are a parent or guardian of a softband user who are at or above the age of majority (AOM). AOM is 21 in Mississippi, 19 in Nebraska and Alabama, and 18 in all other US states.
- Participants provided study-specific consent before completing the survey.
- Users fitted with at least one Ponto Sound Processor on a softband at the time of the survey.

9.1.2 *Exclusion criteria*

The following participants will be excluded from the study:

- Participants who did not provide consent or later revoked consent.
- Under the AOM

9.1.3 *Number of Subjects*

The aim is to enroll 40 participants within 24 months.

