11 STATISTICAL DESIGN AND ANALYSIS

The results of the questionnaires will be analyzed and presented using descriptive statistics including the mean, standard deviation, median, and range.

The sample size in the investigation is not hypothesis-driven, but rather based on the number of users in the database which fit the inclusion criteria as well as estimations derived from previous survey study response rates from social media and other Oticon Medical reach out efforts.

No imputations or estimations will be made to replace missing data.

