23 APPENDICES

A. PEACH

	Question	Never 0%	Seldom 1 - 25%	Sometimes 26 - 50%	Often 51 - 75%	Always 75-100%
1	How often has your child worn his/her hearing aids and/or cochlear implant?	0	1	2	3	4
2	How often has your child complained or been upset by loud sounds?	4	3	2	1	0
3	When you call, does your child respond to his/her name in a quiet situation?	0	1	2	3	4
4	When asked, does your child follow simple instructions or do a simple task in a quiet situation?	0	1	2	3	4
5	When you call does your child respond to his/her name in a noisy situation when he/she can't see your face? (examples of responses include looks up, turns, answers verbally)	0	1	2	3	4
6	When asked, does your child follow simple instructions or do a simple task in a noisy situation?	0	1	2	3	4
7	When you are in a quiet place reading with your child, how often does he/she pay close attention to what you are saying? OR if your child is listening to stories/songs on the TV or CD when there is no other background noise how often can he/she follow what is being said?	0	1	2	3	4
8	How often does your child initiate/participate in conversation in a quiet situation?	0	1	2	3	4
9	How often does your child initiate/participate in conversation in a noisy situation?	0	1	2	3	4
10.	How often does your child understand what you say in the car/bus/train?	0	1	2	3	4

11.	How often does your child recognize peoples' voices without seeing who was talking?	0	1	2	3	4
12.	How often does your child successfully use a phone?	0	1	2	3	4
13.	How often does your child respond to sounds other than voices?	0	1	2	3	4

B. GCBI questionnaire

1. Has your child's Ponto sound processor on softband made his/her overall life better or worse?						
a) much better b) a little better c) no change d) a little worse e) much worse						
2. Has your child's Ponto sound processor on softband affected the things he/she does?						
a) much better b) a little better c) no change d) a little worse e) much worse						
3. Has your child's Ponto sound processor on softband made his/her behaviour better or worse?						
a) much better b) a little better c) no change d) a little worse e) much worse						
4. Has your child's Ponto sound processor on softband affected his/her progress or development?						
a) much better b) a little better c) no change d) a little worse e) much worse						
5. Has your child's Ponto sound processor on softband affected how lively he/she is during the day?						

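### The adapted GCBI items name no comparison state, so parents of children who had an earlier softband or processor may answer against different reference points

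*Combined protocol and SAP*

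**What the plan says.** The Synopsis lists the overall GCBI score as a primary endpoint, and Section 8.1 ties it to benefit after a hearing intervention. Section 9.2.1 describes the GCBI as a retrospective measure and replaces the word operation by the name of the device. Section 6 describes the instrument as "modified to specifically query a child's quality of life after receiving their Ponto sound processor on softband". In Appendix B the first of the 24 items reads "Has your child's Ponto sound processor on softband made his/her overall life better or worse"; the others follow the same pattern, with answers from much better to much worse and a no-change option in the middle.

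On who may take part, Section 5.1 concentrates on Softband 5 but "will also allow for feedback from parents whose children previously or currently use any of the Softband generation models", and it lists three processor families. Section 9.1.1 requires only a current fitting.

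On device history, Appendix C asks for time on a Ponto with softband (question 5), current softband (question 7), whether this is the first softband (question 8, with the option "No, they used a different generation softband in the past") and current processor (question 9). Question 11 opens with "Think about a situation where your child wanted to hear better, before receiving their sound processor" and then asks how much the processor has helped in that situation over the past two weeks.

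Section 11 states: "The results of the questionnaires will be analyzed and presented using descriptive statistics including the mean, standard deviation, median, and range". It names no split by device history.

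**The concern.** The GCBI measures change, and a change score needs a stated starting point. An operation is a dated event and supplies one. A device in continuing use, with successive generations, does not do so for a child who has had more than one of them. A parent whose child moved from an older softband or processor can answer against life with the older device, in which case benefit already gained earlier is reported as no change. Another parent of a similar child can answer against life without a Ponto. The adapted items accept both.

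At stake is what the pooled GCBI mean describes. If some answers are upgrade gains and the rest are gains over no Ponto, the mean belongs to neither question. It also depends on how many experienced users happen to respond. This cannot be repaired once the survey has closed, because no answer shows which reference point the parent had in mind.

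**Working it through.** **No plan figure to reproduce.** The only number is the target: "The aim is to enroll 40 participants within 24 months". Section 11 explains that "The sample size in the investigation is not hypothesis-driven, but rather based on the number of users in the database which fit the inclusion criteria", together with past response rates. It gives no counts, standard deviation (SD) or effect size. The figure of 40 can be neither reproduced nor called wrong, and this point does not depend on it.

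**Reading the instruments side by side.**

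- GCBI (Appendix B): the items contain no comparison state. Because they name the processor and softband together, a change of either could prompt a parent to think of the previous device.
- Question 11 (Appendix C): the word before only selects a situation. The rating is of help over the past two weeks, from not at all to very much, with no no-change option and no negative end. A child who changed only the softband has one literal starting point here. For a child who changed processor, the open matter is which situation the parent recalls.
- PEACH (Appendix A): it rates how often behaviours occur and asks for no comparison, so it is unaffected.
- Device history: question 8 identifies a change of softband generation. Question 9 covers the current processor only. No question covers an earlier processor or another earlier hearing device.

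**How large the mixing could be.** The documents give none of the inputs, so all three are assumptions:

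- u = share of respondents whose child had an earlier device
- r = share of those who answer against the earlier device
- k = upgrade gain divided by gain over no Ponto

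Assume linear scoring with no change at zero, and the same gain over no Ponto in both groups. Then

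pooled mean / gain over no Ponto = 1 − u·r·(1 − k).

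With k = 0.25:

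| u | r = 0.5 | r = 1 |
|---|---|---|
| 10% | 1 − 0.10×0.5×0.75 = 0.963 | 1 − 0.10×0.75 = 0.925 |
| 25% | 1 − 0.25×0.5×0.75 = 0.906 | 1 − 0.25×0.75 = 0.813 |
| 50% | 1 − 0.50×0.5×0.75 = 0.813 | 1 − 0.50×0.75 = 0.625 |

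Over u = 10% to 75%, r = 0.5 to 1 and k = 0 to 0.5, the extremes are 1 − 0.75×1×1 = 0.25 and 1 − 0.10×0.5×0.5 = 0.975. If no parent answers against the earlier device (r = 0), the ratio is 1 and there is no mixing.

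**What a split could show.** The 95% half-width of a mean, in SD units, is t(0.975, n−1)/√n:

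- n = 40: 0.32
- n = 30: 0.37
- n = 20: 0.47
- n = 12: 2.201/√12 = 0.64
- n = 10: 0.72

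For a difference between two groups it is t(0.975, 38)·√(1/a + 1/b): 0.74 SD for 30 against 10, and 0.64 SD for 20 against 20.

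**The case against.** The strongest reply is that the GCBI items name the generic solution, with no model or generation, and so do the objectives. The natural reading is the effect of having a Ponto on a softband at all, and comparing generations is not an objective. The study is also descriptive and uncontrolled, and question 8 already lets softband changers be tabulated without touching the survey. All of this stands. It makes the misreading less likely but does not exclude it, and question 8 misses changes of processor.

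A reader might infer three stronger things, which the documents do not support.

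- That the GCBI and question 11 do mix two kinds of benefit. The wording permits this for the GCBI; nothing shows that it happens. Question 11 is not a before-and-after rating, so the no-change mechanism does not apply to it.
- That the loss can be put at a figure. Taking 12 of 40 previous users, a gain of 1.5 over no Ponto and 0.25 over an earlier Ponto gives (34×1.5 + 6×0.25)/40 = 1.31 if half answer against the old device, and (28×1.5 + 12×0.25)/40 = 1.13 if all do, which is 12.5% to 25% below 1.50. None of those inputs is in the plan.
- That admitting several generations means many previous users. It shows that they can take part, not how many will.

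The remedy has limits too. Anchoring on the first Ponto lengthens recall; question 5 allows for more than nine years of use. It also allows use since birth, where there is no time before. A child who first used some other hearing device still starts from a different baseline, which is why that history should be asked.

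**Conclusion.** The point holds as a gap in wording and reporting. The adapted GCBI has no stated comparator, children with earlier devices are expressly admitted, processor history is not collected, and no split is planned. The pooled mean could therefore combine gain over no Ponto with gain over an earlier device. Whether it will, and by how much, is unknown: the range of 25% to 97.5% reflects assumed inputs only, and no effect at all is also possible. Question 11 is touched marginally and PEACH not at all. This is a cheap improvement to the interpretation of one primary endpoint; it does not call the design or the target of 40 into question.

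**What to change.** 1. Put one sentence above the GCBI items stating the reference point, for example: compared with before your child first used any Ponto on a softband. Add an instruction for children who have used it since birth.
2. Add one question to Appendix C on whether the child used any other sound processor or hearing device before the current one.
3. In Section 11, state that GCBI will be reported descriptively for first-time and previous users, classified by question 8 plus the new item, beside the pooled result. Show respondents who are not sure separately.

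The cost is one sentence with its instruction, one question and one table. The GCBI is already being adapted, and the target number does not change. The downsides are longer recall for long-term users and imprecise subgroup means (95% half-width about 0.6 to 0.7 SD at n = 10 to 12), so the split serves interpretation and should carry no test or claim of difference. The wording must be settled before responses are collected; the split by question 8 alone can be added at any time before analysis.
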